This protocol describes the Avon CAP study and provides information about procedures for entering participants. Every care was taken in drafting this protocol, but corrections or amendments may be necessary in the future. Any amendments will be circulated to and approved by investigators in the study.

The study will adhere to the principles outlined in the UK Policy Framework for Health and Social Care Research. It will be conducted in compliance with the protocol, the Data Protection Act 2018 and other regulatory requirements as appropriate.

Study queries

Clinical and general queries should be directed to the Chief Investigator ([name]) via: [name]; Primary Investigator ([name]) via [name]; or the Clinical research team on [name] or [name].

Sponsor

The University of Bristol is the research sponsor for this study. For further information regarding sponsorship queries, please contact:

Research Governance Team

Research and Enterprise Development

[name]

[name]

[contact] Email: [contact]

Study Summary

Study Title	Avon Community Acquired Pneumonia Surveillance Study: A Pan-pandemic Acute Lower Respiratory Tract Disease Surveillance Study
Short Title	Avon CAP
Clinical Phase	N/A
Study Design	Observational
Study Participants	Patients presenting to North Bristol NHS Trust or University Hospitals Bristol NHS Foundation Trust with features of lower respiratory tract disease (LRTD)
Planned Sample Size	Feasibility phase: 500 per each hospital site Annual sample: 10-15,000 patients per hospital site per annum
Treatment duration	N/A
Follow up duration	1 -2 months following admission
Planned Study Period	3 years
Research question and objectives	The primary objective is to estimate population-based incidence of LRTI (including community-acquired pneumonia hospitalizations) during and after the COVID-19 pandemic, overall and for the subsets associated with SARS-CoV-2, S. pneumoniae , and respiratory syncytial virus. Additional epidemiological and outcomes measures will also be assessed.
Inclusion Criteria	
 1. Aged ≥ 18 years of age 2. Patients hospitalized with illness with following 2 characteristics: 
 a. Acute illness (i.e., present for 28 days or less); AND b. Evidence of acute LRTD: 
 i. Patients with current or suspected COVID-19, or previous proven COVID-19 within last 28 days; OR ii. Clinical or radiologic diagnosis of pneumonia or an acute LRTI; OR iii. New onset or worsening of ≥ 2 of following 8 LRTD symptoms or clinical findings: 
 1. fever ($>38.0^{\circ}\text{C}/100.4^{\circ}\text{F}$) or hypothermia ($<35.5^{\circ}\text{C}$) before or within 24 hours of enrolment 2. pleuritic chest pain; 3. cough (including nocturnal only); 4. sputum production or purulence; 5. dyspnea (shortness of breath) including orthopnea/exertional only; 6. tachypnea (respiratory rate $\geq 20/\text{min}$); 7. abnormal auscultatory findings suggestive of LRTD 8. radiologic finding that is consistent with LRTD, including pneumonia, and/or acute congestive heart failure.
Exclusion Criteria	
 1. Any patient who develops signs and symptoms of LRTD after being hospitalized for ≥ 48 hours (excluding suspected/proven COVID19) 2. Previously enrolled participants readmitted ≤ 7 days after discharge for their study qualifying admission (excluding suspected/proven COVID19) 3. At the time of enrolment, an LRTD-related diagnosis has been excluded or

	another diagnosis confirmed (for example, patient had a fever and tachypnea due to an intraabdominal process such as cholecystitis)
--	---

List of Abbreviations

Abbreviation	Definition
A&E	Accident and emergency
ARI	Acute respiratory illness
BNT162b2	Pfizer/BioNtech COVID-19 vaccine
BRI	Bristol Royal Infirmary
CAP	Community-acquired pneumonia
CHF	Congestive heart failure
COPD	Chronic obstructive pulmonary disease
COVID	Coronavirus disease
CRF	Case report form [eCRF = electronic CRF]
CSA	Clinical study agreement
CT	Computed tomography
CVA	Cerebrovascular accidents
CXR	Chest x-ray
GCP	Good Clinical Practices
ICH	International Council for Harmonisation
ICU	Intensive care unit
IRB/EC	Independent Review Board/ Ethics Committee
LRTD	Lower respiratory tract disease
MRI	Magnetic resonance imaging
NP	Nasopharyngeal
NSTEMI	Non-ST-elevation myocardial infarction
OP	Oropharyngeal
PCV7	7-valent pneumococcal conjugate vaccine
PCV13	13-valent pneumococcal conjugate vaccine
PCV20	20-valent pneumococcal conjugate vaccine
PPV23	23-valent pneumococcal polysaccharide vaccine
RSV	Respiratory syncytial virus
SAP	Statistical analysis plan
STEMI	ST-elevation myocardial infarction
TND	Test Negative Design

UAD	Urinary antigen detection assay
VE	Vaccine effectiveness

1 Background

1.1 Acute lower respiratory tract disease

Acute lower respiratory tract disease (LRTD) encompasses pneumonia, lower respiratory tract infection (LRTI), acute bronchitis, exacerbation of underlying respiratory disease including asthma and chronic obstructive pulmonary disease (COPD). Throughout Europe before the COVID-19 pandemic, the healthcare cost of pneumonia is estimated at approximately €10 billion per annum, with inpatient care accounting for €5.7 billion (European Lung White Book). The indirect costs of lost work-days amount to €3.6 billion. Studies have shown that the incidence of pneumonia in Europe varies by country, age and gender; however, in all studies the incidence of pneumonia increases sharply with age. In the UK, pneumonia affects 0.5 to 1% of adults each year, and the incidence of LRTI is considerably higher with a recent study finding an incidence of 148/1000 person-years in patients \geq 65 years of age (Millet ERC et al). Previous studies to define the disease burden attributable to acute LRTD have used either radiological or microbiological diagnosis to confirm disease, and hence may underestimate the true disease burden, or have been conducted using clinical coding data, which is both retrospective and subject to the errors associated with this methodology. Furthermore, all previous studies have been carried out before the COVID-19 pandemic, and the effect of this new emergent respiratory pathogen on acute LRTD remains unclear.

1.2 COVID-19 infection

In 2019 a novel coronavirus-induced disease (COVID-19) emerged in Wuhan, China. A month later the Chinese Center for Disease Control and Prevention identified a new beta-coronavirus (SARS coronavirus 2, or SARS-CoV-2) as the aetiological agent (Zhu et al, 2019). A worldwide pandemic is currently occurring, and as such the disease burden of acute LRTD will increase. As the responsible virus is a new human pathogen, relatively little is known about disease pathogenesis and the clinical spectrum of disease which it causes, including risk factors associated with poor outcomes in developed countries (Huang et al, 2020).

Furthermore, the interaction between SARS-CoV-2 and other respiratory pathogens including *Streptococcus pneumoniae* and Respiratory Syncytial Virus (RSV) is undefined. It is unknown if bacterial or viral co-infection, superimposed or subsequent infection is common in patients with SARS-CoV-2 infection. This is important in terms of understanding disease pathogenesis and being able to provide appropriate vaccination strategies to try to mitigate mortality and morbidity. It remains unclear how the disease burden of other acute LRTD will be affected, if at all, by the SARS-CoV-2 pandemic.

The UK began vaccinating its adult population in December 2020, using a Department of Health defined risk-based strategy by age, comorbidity and key worker status. Initially, only the BNT162b2 vaccine was used. This is a nucleoside modified messenger ribonucleic acid (modRNA) vaccine from Pfizer/Biontech that encodes the full-length, membrane-anchored spike (S) glycoprotein of SARS-CoV-2 with two introduced proline mutations to lock it in the prefusion conformation (Kariko et al. 2008; Pardi et al. 2015, Wrapp et al. 2020). BNT162b2 showed an acceptable safety profile in a Phase 1/2 study (Walsh et al 2020) and, in a Phase 3 trial conducted in Argentina, Brazil and the United States, was tolerable and demonstrated 95% efficacy against COVID-19 (Polack et al. 2020). At the time of writing, BNT162b2 currently has temporary authorisation for supply under MHRA regulation 174, and data confirming the effectiveness of the vaccine outside of the clinical trial setting are needed. Further, additional COVID-19 vaccines also now have temporary authorisation for supply under regulation 174 in the UK, including from AstraZeneca and Moderna.

1.3 *Streptococcus pneumoniae*

Pneumococcus is a leading cause of lower respiratory tract infections among adults, including community-acquired pneumonia (CAP) population wide (O'Brien, Wolfson et al. 2009, Said, Johnson et al. 2013, Torres, Cillóniz et al. 2018) and among immunocompromised individuals (Zhang, Van Werkhoven et al. 2018), and pneumonia among those with a history of healthcare contact such as long-term care facility residents (Carratala, Mykietiuk et al. 2007, Chalmers, Taylor et al. 2011, Ewig, Klapdor et al. 2012, Polverino, Torres et al. 2013, Parrott, Nebeya et al. 2017). *S. pneumoniae* is also the most frequent bacterial pathogen isolated from patients with acute bronchitis (Macfarlane, Holmes et al. 2001, Creer, Dilworth et al. 2006) and COPD exacerbations (Wilkinson, Aris et al. 2017).

However, previous studies that described the burden of vaccine-preventable pneumococcal pneumonia have largely focused on radiologically confirmed and microbiologically defined CAP only. A recent review of a UK CAP incidence described underestimation of CAP using this approach, potentially by as much as four-fold, due to study requirements for informed consent, study screening processes, radiologic confirmation, and requirement for collection of a dedicated study urine specimen for pneumococcal antigen testing (Chalmers et al., 2017). Correspondingly, a recent vaccine-probe study, performed in the Netherlands, documented that this limited scope appears to underestimate the true burden of respiratory infections prevented by the 13-valent pneumococcal conjugate vaccine (PCV13) (Gessner et al., 2018). The vaccine-preventable disease incidence was 2 to 3.5-fold higher for clinical CAP cases versus microbiologically and radiologically confirmed vaccine-type CAP.

Pneumonia study inclusion criteria are not the only source of underestimation of pneumococcal burden – under or alternate diagnosis also contributes. Presenting complaints as well as signs and symptoms in older patients with pneumonia are often atypical and may lead to missed or incorrect admission diagnoses (Henig & Kaye, 2017). Also, pneumonia may be a secondary to or an underlying cause of the main presenting complaint, such as in patients with altered level of consciousness, cerebrovascular accidents (CVA), congestive heart failure (CHF), or COPD exacerbations. In these scenarios, pneumonia may not be the primary diagnosis code recorded for the hospitalization or may not be coded as an associated diagnosis at all. On this basis, there is a need to assess the burden of pneumococcal disease in the larger group of patients presenting with acute lower respiratory disease – not just those with a formal pneumonia diagnosis. Acute lower respiratory tract disease (LRTD) in adults includes pneumonia (all types); bronchitis; exacerbations of chronic obstructive pulmonary disease, congestive heart failure, asthma, and other underlying pulmonary disease (e.g., cystic fibrosis); acute respiratory distress syndrome (ARDS); and other acute lower respiratory disease, i.e., any condition involving acute lower respiratory pathology (i.e., effects trachea, bronchi, bronchioles, or lungs in opinion of treating/study physician). Comprehensive assessment of all LRTD is needed to identify the disease burden due lower respiratory tract infection.

1.4 RSV infections in adults

RSV is also an important respiratory pathogen later in life, with severe disease occurring among those with compromised cardiac, pulmonary or immune systems and in the elderly (Falsey, Hennessey et al. 2005). Estimates of the RSV disease burden requiring hospitalization in adults are limited but suggest that up to 10% of adults presenting with acute respiratory illness (ARI) during the winter have RSV (Dowell, Anderson et al. 1996, Thompson, Shay et al. 2003, Falsey, Hennessey et al. 2005, Falsey, McElhane et al. 2014, Jain, Self et al. 2015). The RSV season frequently does not completely overlap with the influenza season which confounds the ability to define RSV's clinical and epidemiological features, as viral pathogen testing is often driven by concerns regarding influenza. The limited available data show that age and chronic medical conditions (e.g., COPD, cardiac disease, immunodeficiency) are significant risk factors, and that fever is less commonly observed with RSV than with influenza infection, while cough, dyspnoea, and wheezing may be more common (Falsey 2013, Falsey, McElhane et al. 2014).

1.5 Rationale for study

Accurate incidence rates of acute LRTD and its disease subsets, such as pneumonia and LRTI, remain elusive and the impact of COVID-19 on respiratory disease burden is unclear. Accurate incidence rates of vaccine-preventable infection are required to assess the potential population-level impact of vaccination recommendations. As discussed, current evidence suggests that the burden of pneumococcal and RSV lower respiratory infections is underestimated. Further, the current COVID-19 pandemic due to SARS-CoV-2 has dramatically increased the burden of LRTI worldwide. On this basis, we seek to conduct a study to measure the true burden of acute respiratory disease due to these pathogens during and after the COVID-19 pandemic within the limitations of currently available diagnostic testing.

This population-based multi-hospital, active prospective surveillance is designed to determine population-based incidence rates of hospitalized adults ≥ 18 of age with community-acquired LRTI (including CAP) in Bristol, England. The involved Bristol hospitals' nearly completely capture hospital admissions among residents of a well delineated geographic region allowing for calculation of population-based incidence rates of LRTI. Study data derived from surveillance activities will fully enumerate the number of acute LRTD cases in this region.

Persons identified as having LRTD in study hospitals will be offered participation in the consented portion of this study involving enhanced testing for pneumococcal, RSV, and SARS-CoV-2 infection. This will allow for more complete characterization the incidence of these infections than standard of care testing alone.

Additionally, real world vaccine effectiveness (VE) estimates for COVID-19 vaccines are needed to demonstrate their effect in general populations as well as in risk groups. These can be achieved using a test negative design (TND) case control analysis. For the purpose of these TND analyses, cases are individuals diagnosed with COVID-19 up to 14 days prior to admission or on admission to hospital and controls are those in whom COVID-19 was not detected in the same timeframe. Almost all data needed to conduct these analyses are already being collected in this study, including COVID-19 disease and vaccination status from standard of care records, alongside other medical history and current illness details. To allow for more complete multivariate adjustment for potential confounding differences between the cases and controls, additional information on COVID-19-related behavioural risk factors will be collected from some participants using a standardised questionnaire, such as occupation, frequency of mask use and inclusion in a social bubble. We plan to conduct VE assessments separately for different COVID-19 vaccine products.

1.6 Study Context

This study will undertake surveillance of lower respiratory tract disease (LRTD) including pneumonia in adults in a defined geographical area. This study combines NHS Hospital Trust-based surveillance of lower respiratory tract disease (LRTD) including pneumonia in adults in a defined geographic area with a University-sponsored research study which enhances the diagnostic accuracy in a subset of consented patients. The surveillance will be done in two large hospitals in Bristol and may later be expanded to include a third hospital in Bath. These surveillance activities will be done under NHS Trust governance and with full ethics approval in each hospital. Although originally planned to be stand-alone prospective, comprehensive case ascertainment of adult lower respiratory tract infections within the NHS space, occurring as it turns out in the midst of the coronavirus pandemic, which most commonly presents as pneumonia in adults, the work will be done alongside and overlapping with other observational studies focussed specifically on COVID-19.

The University-sponsored embedded study will recruit a subset of the patients identified during the surveillance activity. Patients who are enrolled, following informed consent, will have additional investigations performed for research purposes and surplus samples obtained during routine case will also be scavenged. The surveillance activity will serve, in effect, as the screening activity for the study as well as providing a comprehensive, anonymised dataset on the disease burden of pneumonia and LRTD in the adult population in the Bristol urban area over a defined time period.

HRA/ethics approval for this embedded study will be sought by the University and both the data from all consented subjects and all the anonymised screening/surveillance datasets will be unified from the databases held by the participating hospitals, with the agreement of those hospitals. These data will be reported on by the University at the end of the project. The combined anonymised dataset, along with the consented patient data and research samples, will belong to the University while the participating hospitals will retain ownership and control over their respective databases and their contents. Thus, the respective institutions will each have autonomy, control, governance oversight and ethical approval jointly and collaboratively for this programme of surveillance and research.

To accurately calculate disease burden and describe acute LRTD and its subsets, it is necessary to record all cases of adults hospitalised within the defined geographical area who meet study criteria. This study will systematically record and describe all adult patients admitted with acute LRTD and its subgroups, providing an accurate calculation of disease incidence, burden and outcome analysis in addition to other epidemiological analyses, including identifying risk factors for disease and poor outcome.

This study will recruit a subset of the patients identified during the surveillance activity into a consented arm. Patients who are enrolled, following informed consent, will have additional investigations performed for research purposes and surplus samples obtained during routine care will also be scavenged. Participants recruited to the embedded study will be asked to consent to the use of their data for clinical research, with a target enrolment of up to 80% of eligible admitted patients. Patients approached with information about the consented study will subsequently fall into 3 groups:

[figure not shown]
- Those who provide full consent to the study, including access to medical data
- Those who provide consent to access to medical data only (and not biological samples)
- Those who decline consent and are not enrolled in the study, and are only noted in the screening log

Individuals who decline consent for access to medical data will not be recruited to this non-consented study arm, thereby ensuring there is no contagion of the non-consented study arm. In this way, the non-consented surveillance will only collect medical data from individuals in whom it is not practicable to take consent.

However, as it is not practicable for the research team to approach and consent every individual hospitalised with acute LRTD into the consented arm, this study seeks approval for data collection to be undertaken on these individuals via a non-consented surveillance arm. We therefore will request and obtain authorisation for access to personal data under Section 251 of the NHS Act 2006 for the use of non-consented data. If patients are eligible, data fields from their routine clinical care would be collected to determine features of clinical presentation and disease, including co-morbidities, routine healthcare tests and outcomes (e.g. requirement for intensive care and/or organ support, mortality).

The data collected during the non-consented surveillance activity will be combined with the data obtained from the consented arm to provide a comprehensive dataset of patients with acute LRTD. In this way, all patients and disease will be captured and described, allowing for a complete and accurate estimation of disease incidence and burden.

Study Flow Diagram: Activities pertaining to data collection for consented study & non-consented surveillance arms, demonstrating how they work together.

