Study procedures and **Error! Reference source not found.** sections of the protocol for detailed information on each procedure and assessment required for compliance with the protocol.

Consented Arm

The investigator may schedule visits (unplanned visits) in addition to those listed in the schedule of activities table, in order to conduct evaluations or assessments required to protect the well-being of the participant. Collection of standard-of-care data will be done for all identified LRTD events in study hospitals and entered into the surveillance databases hosted by the Trusts. This will be conducted by appropriate members of the clinical team, and research team members will only have access to pseudonymised data. Sample collection and interview activities shown in bold below will be undertaken for consented participants only by members of the research team.

Table 1. Comprehensive List of Procedures by Visit for Consented-Arm, Including Visit Windows.

Procedure / Assessment ^a	Screening/ Enrolment Visit ^b	Final Assessment/ Vital Status (Data Collection only)	Convalescent Visit ("Serology Subset" Only) ^e	Mortality Assessment (data collection only)
	Visit 1	Visit 2	Visit 3	Visit 4
	Day 1	Day 30	Day 45	Day 365
Visit Window	Within 48 hours of admission	Day 30 to 45	Day 22 to 60^c	Day 365
Screening (surveillance)	X			
Clinical symptoms	X			
Medical History ^c	X	X	X	
Vaccination History	X		X	
CRB-65 and pneumonia severity (PSI) score	X			
Informed Consent	X			
Eligibility confirmation for embedded study	X			
Patient Interview, including approved questionnaires^f	X		X	
Collect urine specimen	X			

Procedure / Assessment ^a	Screening/ Enrolment Visit ^b	Final Assessment/ Vital Status (Data Collection only)	Convalescent Visit ("Serology Subset" Only) ^e	Mortality Assessment (data collection only)
	Visit 1	Visit 2	Visit 3	Visit 4
	Day 1	Day 30	Day 45	Day 365
Collect upper respiratory tract sample for SARS-CoV-2, RSV and other pathogens^d	X		X ^d	
Collect blood specimen^e	X		X	
Obtain residual (scavenged) standard care specimens from clinical laboratory	X	X	X	
Record SOC respiratory specimen testing results	X			
Record SOC blood culture results	X			
Record SOC chest imaging results	X			
Final acute LRTD Illness Diagnosis		X		
Cardiac complications		X		
Vital Status/Mortality		X		X
Hospitalization duration, readmission, & level of care		X		
Collect Research-related Injuries (RRIs)	X	X	X	

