Avon CAP will undertake systematic and comprehensive surveillance of all adults hospitalized with acute lower respiratory tract disease within a well-defined geographical area. As the demographic and population of Bristol is well described, ascertaining the true burden of acute respiratory infection and describing disease in the context of COVID-19 will allow this study to calculate accurate estimates of incidence. In order to be able to determine the morbidity and mortality associated with acute lower respiratory tract disease, it is necessary that the data collected cover the entire population, as missing any cases within the study area would result in an inaccurate calculation of disease burden. Furthermore, by capturing and detailing precise clinical data, this study will be able to stratify disease by patient factors such as age, gender and ethnicity, as well as by risk factors, including smoking status and pre-existing co-morbid disease including chronic respiratory and cardiovascular conditions. Through this surveillance mechanism all acute respiratory infection in hospitalized adults will also be described by causative pathogen and radiological diagnosis, in addition to capturing patient outcome. The study has three important features:

1. The data will be comprehensive and complete over a defined time period for a defined population area and therefore not subject to the potentially biased ascertainment which weakens other large studies
2. The demographic of the study area is broad in terms of deprivation, minority groups, urban and rural distribution and is in many ways highly representative of the population of England, permitting results to be of value for nationwide planning.
3. The study has substantial confirmed funding which will underpin its viability and successful conduct and is fully embedded within the clinical services of the contributing hospitals, while the anonymised data handling and analysis will be undertaken within the University domain thus not competing for scarce research resources at a time of critical need within the NIHR and NHS research infrastructures.

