9.4.2 Representativeness

Hospitalized individuals admitted with LRTD who meet the eligibility criteria will be invited to participate in the enhanced diagnostic testing portion of the study. It is possible there could be bias in the refusals being different from those who do take part, for example those with most severe disease. Further, if recruitment for enhanced diagnostic testing cannot be performed at all times (eg, weekends, overnights, and holidays), some patients with acute LRTD may not be able to participate in the enhanced diagnostic testing portion of the study on that basis. The representativeness of enhanced diagnostic testing participants will be established by comparing the groups that have accepted and declined using eCRF data.

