10.7 Consent

Consented arm

In line with applicable regulations, consent will be obtained (as specified above) for access to patient data and to obtain clinical specimens.

Non-Consented arm

In line with applicable regulations, Confidentiality Advisory Group approval under Section 251 of the NHS Act 2006 will be sought to obtain patient records without consent. This will only apply to individuals who are eligible for the study but who could not be approached to discuss or seek consent to participate in the consented study. Therefore, Section 251 of the NHS Act will only apply to those individuals in whom it is not practicable to obtain consent e.g. those who died or were discharged before the research team could approach them. For participants enrolled in the embedded enhanced diagnostic study arm, consent will be obtained for access to patient data. Individuals approached by the research team to discuss and seek consent for the embedded enhanced diagnostic study will subsequently fall into three categories:

- Those who provide full consent to the study, including access to medical data
- Those who provide consent to access to medical data only (and not biological samples)
- Those who decline consent and are not enrolled in the study, and are only noted in the screening log

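### Under the protocol's consent rules, patients who refuse data access drop out of the incidence numerator but stay in the denominator, contrary to its completeness claims and to its own statements on data collection

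*Protocol*

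**What the plan says.** Section 1.6 sorts approached patients into three groups: full consent, consent to medical data only, and refusal. The third group is described as "Those who decline consent and are not enrolled in the study, and are only noted in the screening log", and Section 10.7 repeats this. Section 1.6 adds: "Individuals who decline consent for access to medical data will not be recruited to this non-consented study arm". Section 10.7 restricts the Section 251 route in the same sense: "This will only apply to individuals who are eligible for the study but who could not be approached to discuss or seek consent".

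The analysis dataset is the consented arm plus the non-consented arm. Of that combination Section 1.6 says that "all patients and disease will be captured and described, allowing for a complete and accurate estimation of disease incidence and burden". Section 1.5 states: "Study data derived from surveillance activities will fully enumerate the number of acute LRTD cases in this region". Section 5, which justifies access without consent, warns that "missing any cases within the study area would result in an inaccurate calculation of disease burden".

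Other sections describe data capture without any exception for refusal. Section 2 says, for both arms: "Collection of standard-of-care data will be done for all identified LRTD events in study hospitals". Section 4.1 says the same of all LRTD events, and Section 4.4.5 says that individual consent is not needed to collect screening data.

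On refusal as a source of bias, Section 9.4.2 plans this check: "The representativeness of enhanced diagnostic testing participants will be established by comparing the groups that have accepted and declined using eCRF data".

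**The concern.** The primary outcome (Section 3.1) is a population-based incidence of LRTI hospitalization, overall and for pneumonia. A patient who is admitted, approached and refuses data access belongs to the catchment population and is a case, but under Sections 1.6 and 10.7 enters neither arm. Section 9.2.2 defines LRTI for an enrolled subject by final diagnosis, laboratory result or clinical findings. A decliner is not enrolled, and a log entry is not said to hold any of those items.

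Each such patient therefore lowers the estimated rate, always in the same direction. The limitations section does not name this loss. Section 9.4.2 treats refusal as a question of who receives enhanced testing. Section 9.4.3 covers patients missed through pathway, timing or human error and regards those misses as random. The protocol describes no step that returns decliners to the numerator.

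**Working it through.** **Inputs (Section 9.1):** 23,000 patients a year across two sites; about 630,000 adults; stated incidence 3.65 per 100 person-years, 95% CI 3.60 to 3.70. **Input (Section 1.6):** target enrolment of up to 80% of eligible patients. **Assumed:** d, the share of eligible patients who refuse data access altogether. The protocol gives no value.

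**Step 1. Reproduce the plan's figure.**
- Rate = 23,000 / 630,000 = 3.651 per 100 person-years.
- Poisson 95% limits = (23,000 ± 1.96 × √23,000) / 630,000 = (23,000 ± 297) / 630,000 = 3.604 to 3.698.

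This matches the stated 3.65 (3.60 to 3.70), so the planning figure is arithmetically correct.

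**Step 2. Effect of omitting decliners.** If 23,000 is the true eligible total, the observed rate is 23,000 × (1 − d) / 630,000.

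| d (assumed) | Patients omitted | Patients recorded | Rate per 100 person-years | 95% CI |
|---|---|---|---|---|
| 1% | 230 | 22,770 | 3.61 | 3.57–3.66 |
| 2% | 460 | 22,540 | 3.58 | 3.53–3.62 |
| 5% | 1,150 | 21,850 | 3.47 | 3.42–3.51 |
| 10% | 2,300 | 20,700 | 3.29 | 3.24–3.33 |

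**Step 3. Where bias overtakes stated precision.** The half-width is 297 patients, and 297 / 23,000 = 1.3%. Above that share the shortfall is larger than the half-width.

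**Step 4. Upper bound.** If the 80% target is met, at most 20% could be decliners, giving 18,400 / 630,000 = 2.92. This is a ceiling and not an estimate, because the other 20% also includes patients who could not be approached, and the non-consented arm captures those.

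**Step 5. Set the sections side by side.**
- Sections 1.6 and 10.7: refusers appear in the log only, and the non-consented arm is closed to them.
- Sections 2, 4.1 and 4.4.5: standard-of-care data on all events, with no consent needed for screening data.
- Sections 1.5, 1.6 (on combining the arms) and 5: capture is complete.

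If the first group governs, the third is untrue. If the second governs, data are held on people who were told they would only be noted in a log.

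**Step 6. The Section 9.4.2 check.** Under Sections 1.6 and 10.7, full refusers have no eCRF record to compare. Patients who consent to medical data only do have one.

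**The case against.** The strongest reply is that loss of decliners is not settled. Section 2 has the clinical team enter data on all identified events in Trust databases, with researchers seeing only pseudonymised data. Section 4.3 assigns a surveillance number after the admission list is screened, without mention of consent. Section 1.6 also speaks of unifying all anonymised screening and surveillance datasets. A reader might infer from the decliner rules that these patients are certainly lost. The protocol does not support that, because it says both things. What stands is the contradiction, and the shortfall if the decliner rules prevail.

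Four other strong readings should also be resisted.
- **That the accepted-versus-declined comparison cannot be done at all.** It can be done for data-only consenters, who declined samples; only full refusers are out of reach.
- **That refusal is known to vary with severity.** Section 9.4.2 raises this as a possibility, with severe disease as an example, so unequal distortion across strata is a risk and not an established fact.
- **That a fifth of cases will be missed.** The 20% is a ceiling, as shown above.
- **That nothing will ever correct the count.** The log may allow a head count, and Section 9.3 leaves detailed methods to a SAP that is not at hand. It can be said only that the protocol describes no correction and claims completeness.

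The yardstick is also limited. The interval in Section 9.1 belongs to an all-LRTD planning rate and not to the primary LRTI outcome. It is also very narrow: Section 9.4.1 already accepts that the denominator correction will be by estimation, and an error of 1.3% there would matter as much. That limits what the half-width comparison shows, but it does not remove a bias of known direction.

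**Conclusion.** The point holds in this form. The decliner rules in Sections 1.6 and 10.7, with the LRTI definition in Section 9.2.2, omit full refusers from the numerator and leave them in the denominator. That conflicts with the completeness claims in Sections 1.5, 1.6 and 5, and the data-collection statements in Sections 2, 4.1 and 4.4.5 contradict the decliner rules themselves.

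If the decliner rules prevail, the rate is understated in proportion to d. The size rests on an assumed d and on 23,000 being the full eligible total. A head count could repair the crude LRTD total. It could not classify decliners as LRTI, pneumonia or pathogen-specific cases, and those are what the primary outcome and most secondary outcomes require. The matter should be settled before incidence is reported.

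**What to change.** 1. Reconcile Sections 1.5, 1.6 (on combining the arms), 2, 4.1, 4.4.5, 5 and 9.4.2 with the decliner rules in Sections 1.6 and 10.7, so that the protocol states once whether any data on full refusers are held and used.
2. If their data are not used, count them from the existing screening log without medical data: by site and month, and by age band and sex if approvals allow. Add the count to the LRTD numerator.
3. For LRTI, CAP and pathogen subsets, weight recorded patients within strata by eligible / recorded, and report unweighted results alongside. At an assumed 5% refusal in a stratum, the weight is 1 / 0.95 = 1.053.
4. Restate the Section 9.4.2 check as full consent versus data-only consent versus non-consented arm, with the decliner count shown beside them.
5. List refusal in Section 9.4 as a limitation of the incidence numerator.

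**Cost:** amended text, a tally in a log already kept, and one stratified weight. The tally may need its own approval, since it uses information about people who refused. The weighting assumes that decliners resemble recorded patients within strata; the data cannot test this, and it would fail if refusal does depend on severity. For that reason the unweighted results should stay in view.
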